1.2 Rationale for Study[†]

Food and Drug Administration (FDA)/Center for Biologics Evaluation and Research (CBER) recommends a 15-year time-period for follow-up observations. However, CBER also recognizes that assessment of risk is a continuous process, and the nature and duration of follow up observations may be revised accordingly.⁴ This follow up protocol is to assess the long-term safety of OZ1/LNL6 gene transfer product in patients who were enrolled in the OTH/OZ1-INT-1 study. Based on the integrated safety analysis of observations up to 10 years in this LTFU study, up to 15 years with the same OZ1/LNL6 gene transfer product in 2 Phase 1 LTFU studies (OZ1-HV1-101 and OZ1-HV1-102), and published reports of adverse events observed with gene therapeutic products using the same type of retroviral vector,^{2,3,5,6,7,8,10,11,12} the sponsor has determined that the risk to OZ1/LNL6 gene transfer product to recipients beyond 10 years post-infusion is minimal. Accordingly, this long term follow up study will conclude by 30 November 2017. This completion date represents a minimum of 10 years follow up following the receipt of OZ1/LNL6-modified CD34+ cells.

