### **8.2.4. Summary of Time Adjusted Related SAEs by System Organ Class and Preferred Term**

The number of related SAEs will be presented by system organ class and preferred term. In addition, event rate per year will be calculated using the formula below:

$$\text{Event rate per year} = \text{Number of related SAEs} / \text{Patient years in long term follow-up}$$

Where patient years in long term follow-up is calculated individually for each patient using the last available date of a safety assessment – (date of infusion + 2 yrs) and summed over all patients.

Each value from the above derivation will be totaled over each body system and preferred term to give a rate at which a particular related SAE may be experienced by a patient in a given year *ie* a patient rate per year of 1 for a particular preferred term is equal to a patient experiencing a related SAE once a year for the particular preferred term.

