### **8.2.5. Correlation between Frequency of SAEs and NSRAE and Time on Study**

Correlation between OZ1 & LNL6 DNA-PCR (%) and the frequency of SAEs and NSRAEs will be assessed using PROC CORR in SAS. The number of patients on study and experiencing at least one SAE at the timepoints 2.5, 3, 3.5, 4, 4.5, 5, > 5 to ≤ 10 and > 10

<Protocol: Janssen OZ1-HV1-101/102/202>

<INC code: 1003733>

<SAP Version: 3.0>

---

years post infusion will be presented. In addition Spearman's rank correlation co-efficient and its associated p-value overall timepoints will be presented. Similar presentations will be made for patients experiencing at least one NSRAEs.

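### The SAP's only person-time rate pools all years from year 2, so an excess of related SAEs after year 10 is diluted, and no rate or interval is planned for that period

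*SAP*

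**What the plan says.** **The rate.** SAP 8.2.4 divides the number of related SAEs by patient-years in long-term follow-up. A patient's time is the "last available date of a safety assessment – (date of infusion + 2 yrs) and summed over all patients". The values are then totalled by system organ class and preferred term "to give a rate at which a particular related SAE may be experienced by a patient in a given year". Shell 14.3.4 shows events and rate by study and overall. It has no split by time since infusion, no patient-years and no interval. The Index of Tables assigns it to the Safety population, which under SAP 4.1 does not require receipt of product.

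**Other outputs that reach past year 10.**
- SAP 8.2.5 promises "The number of patients on study and experiencing at least one SAE at the timepoints" listed there, the last two being more than 5 to 10 years and more than 10 years. The same is planned for non-serious related events.
- SAP 8.5 and shells 14.4.1 to 14.4.6 give the percentage of patients answering yes at each visit on new malignancies, haematological disorders and similar questions, with a visit-specific denominator.
- Individual events and deaths are listed.

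**The closing rationale.** Protocol 1.2 states that "the sponsor has determined that the risk to OZ1/LNL6 gene transfer product to recipients beyond 10 years post-infusion is minimal". The stated basis begins "Based on the integrated safety analysis of observations up to 10 years in this LTFU study, up to 15 years with the same OZ1/LNL6" and goes on to name two Phase 1 follow-up studies and published reports.

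**The concern.** Dividing all events by all patient-years and reading the result as a yearly risk assumes the same risk in every year since infusion. The study exists because vector effects, insertional oncogenesis above all, may come late. If risk rises after year 10, the rise is averaged with eight earlier years per patient (years 2 to 10) and largely disappears. If no late events occur, a zero set against the pooled denominator looks far more precise than the late experience allows.

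The final analysis is where the 202 follow-up beyond year 10 can be put into numbers, in a study that stops short of the 15 years that Protocol 1.2 reports as the regulator's recommendation. As planned, a reader of the final report would get no late rate, no late patient-years and no limit on what the late data exclude.

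**Working it through.** The documents give no rate, event count or sample size to reproduce. What follows is an illustration with its assumptions stated.

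**Inputs**
- *Follow-up of the last-infused patient.* SAP 6.1 puts the cut-off for the last subject's year-10 visit at 13 Feb 2016 (SAP 1.1: February 2016). I infer a last infusion in 202 about 13 Feb 2006. Study end is 30 Nov 2017 (Protocol 1.2). That is 4,308 days / 365.25 = 11.79 years.
- *Recipients.* Protocol 1.1: approximately half of 74 received OZ1, so about 37, or 38 with the one patient enrolled under the earlier LNL6-versus-OZ1 design. The number entering follow-up is not given.
- *Attrition and individual infusion dates.* Not given, so varied below.

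**Share of person-time beyond year 10**

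A patient followed to T years contributes T − 2 patient-years, of which T − 10 are late. The late share is s = (T − 10)/(T − 2).

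At T = 11.79: s = 1.79/9.79 = 0.183.
- 37 recipients: 37 × 1.795 = 66 late of 37 × 9.795 = 362 patient-years.
- 38 recipients: 68 of 372.

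**Dilution**

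An excess confined to years beyond 10 enters the pooled rate multiplied by s, so it is diluted 1/s-fold: 1/0.183 = 5.5.

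| Scenario | Dilution of a late excess |
|---|---|
| All followed to T = 11.79, no loss | 5.5 |
| T = 12 / 13 / 15, no loss | 5.0 / 3.7 / 2.6 |
| Infusions spread evenly over 1 / 2 / 3 / 4 years ending Feb 2006, no loss | 4.5 / 3.9 / 3.4 / 3.1 |
| T = 12, loss of 2% / 5% / 10% per year from year 2 | 5.4 / 6.2 / 7.8 |
| T = 11.79, loss of 10% per year | 8.5 |
| T = 12, 37 placebo patients adding 0.5 to 2 years each to the denominator | 5.25 to 6.0 |

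With loss at rate h, person-time from year a to year b is proportional to [exp(−h(a−2)) − exp(−h(b−2))]/h.

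The factor applies to the excess, not to the whole late rate. For a k-fold rise after year 10, the pooled rate is 1 + s(k − 1) times the early rate. With k = 5 and s = 0.183 that is 1.73, so the late rate is understated 5/1.73 = 2.9-fold, not 5.5-fold.

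**Zero-event precision**

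The one-sided 95% Poisson upper limit with no events is −ln(0.05)/PY = 2.996/PY.

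| Recipients | Beyond year 10 | Pooled from year 2 |
|---|---|---|
| 37 | 2.996/66.4 = 4.5 per 100 patient-years | 2.996/362.4 = 0.83 per 100 |
| 38 | 2.996/68.2 = 4.4 per 100 | 2.996/372.2 = 0.80 per 100 |

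Any loss to follow-up raises these limits.

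**Do the other outputs fill the gap?** Text and shell disagree in 8.2.5. The text speaks of patients on study, but shell 14.3.5 shows only patients with at least one event, Spearman's rho and a p-value. The heading concerns time on study, while the text correlates events with DNA-PCR (%). The 8.5 percentages have a denominator at each visit but no person-time, no interval and no total for the period beyond year 10.

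**The case against.** The strongest reply has four parts.

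1. **Late risk is not ignored.** A reader might infer that risk beyond year 10 is never estimated. The documents do not support that. SAP 8.2.5 plans counts for more than 10 years, on its natural reading with a denominator. SAP 8.5 reports new malignancies visit by visit, split in the shells into related and not related. The missing number on study in shell 14.3.5 is a mismatch between text and shell, not an absent analysis. This stands. What is missing is a person-time rate and an interval.
2. **The closing statement does not cite this rate.** A reader might infer that the pooled rate is what supports closing the study. Protocol 1.2 cites an integrated safety analysis, Phase 1 follow-up and published reports, and the determination precedes the final analysis expected in 2018. The integrated analysis is not among the documents, and it may have been split by time. This also stands.
3. **Evidence beyond year 10 need not be Phase 1 only.** A reader might infer so from the wording about observations up to 10 years in 202. But the 2016 analysis ran to the last subject's year-10 visit, so patients infused earlier could already have passed year 10, and the amendment came about 16 months later. A limit computed on Phase 1 recipients alone would rest on a loose phrase and an assumed event count.
4. **The plan is descriptive and small.** No sample size was calculated, and banding every preferred term would give mostly empty cells. That is a fair limit on the remedy. It does not justify reading a pooled rate as a yearly risk.

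**Conclusion.** The point holds in a limited form. The only person-time rate in the SAP assumes constant risk since year 2, in a study of delayed effects. For years beyond 10 the plan offers crude counts and per-visit percentages, without a rate or an interval.

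Under the stated assumptions, less than a fifth of the 202 recipients' patient-years lie beyond year 10, and the zero-event limit for that period is about 5.5 times the pooled one. No single dilution factor should be quoted as a finding: it runs from about 2.6 to 8 (8.5 at the extreme of the scenarios tried), depends on follow-up and attrition that the documents do not give, and applies only to the late excess.

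The point does not show that the sponsor's judgement of minimal late risk is wrong, nor that it was drawn from this rate. It shows that the planned final analysis will not quantify the late period. The change is worth making before the final tables are produced.

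**What to change.** - **Table 14.3.4.** Keep the table. Add rows for all related SAEs combined, and for malignancy, by time since infusion: 2 to 5, more than 5 to 10, and more than 10 years. The cut points at 5 and 10 years are already in SAP 8.1. For each band show events, patient-years and an exact Poisson interval or upper limit, including bands with zero events. Restrict these rows to product recipients (the PP population of SAP 4.2), so that placebo patients' early time does not enter the denominator.
- **SAP 8.2.4.** State that the pooled figure is an average over the follow-up observed.
- **Shell 14.3.5.** Add the number on study in each period, as the text of 8.2.5 promises.
- **Final report.** Beside any conclusion about the period beyond year 10, give the number of recipients and patient-years observed there and the upper limit.

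**Cost.** A short SAP revision and a little programming. The infusion date and last assessment date are already needed for 8.2.4, and 8.2.5 already requires events to be placed in time. Cells will be sparse, which is why only the overall and malignancy rows should be banded. The stated late figure will look less favourable than the pooled one.

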### **8.2.5. Correlation between Frequency of SAEs and NSRAE and Time on Study**

Correlation between OZ1 & LNL6 DNA-PCR (%) and the frequency of SAEs and NSRAEs will be assessed using PROC CORR in SAS. The number of patients on study and experiencing at least one SAE at the timepoints 2.5, 3, 3.5, 4, 4.5, 5, > 5 to ≤ 10 and > 10

<Protocol: Janssen OZ1-HV1-101/102/202>

<INC code: 1003733>

<SAP Version: 3.0>

---

years post infusion will be presented. In addition Spearman's rank correlation co-efficient and its associated p-value overall timepoints will be presented. Similar presentations will be made for patients experiencing at least one NSRAEs.

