## 7. EFFICACY

### 7.1. MARKING IN PERIPHERAL BLOOD MONONUCLEAR CELLS

PBMC analysis (OZ1 & LNL6 DNA PCR (marking)) will be performed at 2 years post infusion or the nearest timepoint before starting the long term follow-up and at each 6 monthly visit up to 5 years post infusion and annually there after. Analyzed samples for gene detection will be classified as either not done, not detected or detected. If detected genes are found these will further be classified as to whether they are below the limit of quantification or not. Samples below the limit of quantification will be classified as either 1/3 (genes detected in 1 of the 3 triplicates of the sample), 2/3 (genes detected in 2 of the 3 triplicates of the sample) or 3/3 (genes detected in 3 of the 3 triplicates of the sample). For samples above the limit of quantification the percentage detected will be recorded for OZ1 & LNL6 DNA-PCR.

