### 7.2. METHODS OF ANALYSIS

#### 7.2.1. Analysis of Marking in Peripheral Blood Mononuclear Cells

For OZ1 & LNL6 DNA-PCR (marking) the number and percentage of patients in each of the categories Not Detected, Detected (1/3 Detected, 2/3 Detected, 3/3 Detected) and Detected (Quantifiable). The number and percentage of patients in each category will be presented at each timepoint for 102/202 combined and overall for the PP population.

Patients who have quantifiable OZ1 & LNL6 DNA-PCR detected will have the value listed and the relationship between the % marking and calculated dose, age at infusion, gender and race explored as described below.

Correlation between OZ1 & LNL6 DNA-PCR (%) and calculated dose will be assessed using PROC CORR in SAS. The number of patients with quantifiable detected and calculated dose data, Spearman's rank correlation co-efficient and its associated p-value will be presented. Similar presentations will be made for OZ1 & LNL6 DNA-PCR (%) versus age and OZ1 & LNL6 DNA-PCR (%) and time since infusion (as defined in Section 6.3).

Association between the number of patients with and without OZ1 & LNL6 DNA-PCR quantifiable detection and gender will be assessed by the Chi-Squared test using PROC FREQ in SAS. The number of patients with data for both parameters, the Chi-Square statistic and its associated p-value will be presented. A p-value of less than 0.05 will indicate an association between the parameters. Similar presentations will be made for OZ1 & LNL6 DNA-PCR versus race and gender. If it is not appropriate to perform the Chi-Square test due to small cell sizes, Fishers Exact test will be performed.

<Protocol: Janssen OZ1-HV1-101/102/202>

<INC code: 1003733>

<SAP Version: 3.0>

---

The above analyses will be performed for 102/202 combined and overall at each post infusion timepoint for the PP population providing there are patients with quantifiable data to render the analyses meaningful. A review of the marker data will take place at the Data Review Meeting. All decisions taken regarding the above analyses will be fully documented in the meeting minutes.

The percentage of patients detected with either a quantifiable or non quantifiable OZ1 & LNL6 DNA-PCR result will be plotted over time for 101, 102 and 202 separately, 102/202 combined and overall for the PP population.

<Protocol: Janssen OZ1-HV1-101/102/202>

<INC code: 1003733>

<SAP Version: 3.0>

---

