### 8.2. ADVERSE EVENTS

Throughout the long term follow-up, all serious adverse events (SAEs) and non-serious related adverse events (NSRAEs) observed by medical staff, or reported by the patient, will be evaluated by the investigator and noted in the adverse event section of the CRF.

SAEs and NSRAEs will be coded using the current Medical Dictionary for Regulatory Activities (MedDRA). SAEs and NSRAEs will be summarized separately for 101, 102 and 202 and overall by tabulating the frequency of reports for each unique event and by tabulating the number of patients experiencing one or more events. The denominator used for the calculation of percentages will be the number of patients in the Safety population for the respective long term follow-ups. SAEs and NSRAEs will be summarized by MedDRA system order class and preferred term. Separate data listings of all information relating to patient death, SAEs and NSRAEs will be provided.

SAEs are defined as events that have a seriousness category of death, life threatening, initial or prolonged hospitalization, disability, congenital anomaly or other medically important condition such as predominant integration site, positive RCR, malignancy or abnormal pregnancy outcome (*ie* recorded seriousness category of 1, 2, 3, 4, 5 or 6). AEs recorded as non-serious (7) will be defined as non-serious and will only be recorded if they are considered related to the gene transfer product. A related AE is defined as any

<Protocol: Janssen OZ1-HV1-101/102/202>

<INC code: 1003733>

<SAP Version: 3.0>

AE whose relationship to the gene transfer product is recorded as possible, probable or very likely (coded on CRF as 3, 4, or 5). Severe AEs are defined as any AE recorded in the 'severe' category (coded on CRF as 3). AEs leading to death are defined as any AE in the seriousness category of 'death' (coded on CRF as 1) and/or an outcome category of 'fatal' (coded on CRF as 5). NSRAEs are defined as adverse events (AEs) whose seriousness category is recorded as non-serious but are considered to have a possible, probable or very likely relationship to the gene transfer product.

If the severity or relationship of an SAE/AE is missing a worst case scenario will be assumed (*ie* the AE will be set to severe or very likely, respectively).

The following AE summary tables will be presented 101, 102, 202 and overall.

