### 13. INDEX OF TABLES

Table Number	Table Description
14.1.1	Patient Disposition Including Reason for Discontinuation Summary Statistics: All Patients
14.1.2	Analysis Populations Summary Statistics: All Patients
14.1.3	Demographic Details Age, Gender and Race Summary Statistics: PP Population
14.1.4	Significant Medical History Time Since HIV-1 Infection Summary Statistics: PP Population
14.1.5	Treatment Details Summary Statistics: PP Population
14.1.5a	Treatment Details (Study 202 only) Summary Statistics: PP Population
14.1.6	Compliance Visit Attendance Summary Statistics: PP Population
14.2.1.1	OZ1 and LNL6 DNA PCR Marking Parameters (PBMC) Over Time: Actual Values Summary Statistics: PP Population
14.2.1.1a	OZ1 and LNL6 DNA PCR Marking Parameters (PBMC) Over Time: Actual Values (Study 202 only) Summary Statistics: PP Population
14.2.1.2	OZ1 and LNL6 DNA PCR Relationship of Marking Parameters (PBMC) with Calculated Dose, Age, Time on Study, Gender and Race Statistical Analysis: PP Population
14.2.1.2a	OZ1 and LNL6 DNA PCR Relationship of Marking Parameters (PBMC) with Calculated Dose, Age, Time on Study, Gender and Race (Study 202 only) Statistical Analysis: PP Population
14.3.1	Overall Summary of Adverse Events Summary Statistics: Safety Population
14.3.2	Serious Adverse Events By System Organ Class, Preferred Term, Severity and Relationship including Patient ID Summary Statistics: Safety Population
14.3.3	Serious and Non Serious Related Adverse Events By System Organ Class, Preferred Term, Outcome and Relationship including Patient ID Summary Statistics: Safety Population
14.3.4	Time Adjusted Serious Adverse Events By System Organ Class and Preferred Term Summary Statistics: Safety Population
14.3.5	Serious and Non-Serious Related Adverse Events Relationship Between Time on Study and Related Serious and Non Serious Adverse Events Summary Statistics: Safety Population

<Protocol: Janssen OZ1-HV1-101/102/202>

<INC code: 1003733>

<SAP Version: 3.0>

14.3.6	Patient Death By System Organ Class and Preferred Term, Including Patient ID Summary Statistics: Safety Population
14.4.1	Clinical History Experienced new or exacerbated pre-existing haematological disorders (including clinically significant laboratory abnormalities)? Summary Statistics: PP Population
14.4.2	Clinical History Had any new malignancies (including skin cancers)? Summary Statistics: PP Population

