SYSTEM ORGAN CLASS A												
PREFERRED TERM 1												
PREFERRED TERM 2												
ETC												

Note: Data summarized in this table are presented in data listing X.X.X.X  
 NR = Not related (those events with a relationship of not related or doubtful)  
 Rel = Drug-related adverse events (those events with a relationship of possible, probable or very likely)

DDMMYYYY HH:MM

*Prgm note: This table will continue for Fatal and Unknown categories and for OZ1-HV1-102, OZ1-HV1-202 and Overall*

<Protocol: Janssen OZ1-HV1-101/102/202>

<INC code: 1003733>

<SAP Version: 3.0>

Janssen - OZ1-HV1-101/102/202

TABLE 14.3.4

Page 1 of x

Time Adjusted Serious Adverse Events  
By System Organ Class, Preferred Term  
Summary Statistics: Safety Population

System Organ Class Preferred Term	OZ1-HV1-101	OZ1-HV1-102	OZ1-HV1-202	Overall
SYSTEM ORGAN CLASS 1				
Number of events				
Event rate per year				
PREFERRED TERM 1				
Number of events				
Event rate per year				
PREFERRED TERM 2				
Number of events				
Event rate per year				
SYSTEM ORGAN CLASS 2				
Number of events				
Event rate per year				
PREFERRED TERM 1				
Number of events				
Event rate per year				
ETC				

Note: Data summarized in this table are presented in data listing X.X.X.X  
Event rate per year = Number of related SAEs / Patient years in long term follow-up

*DDMMYYYY HH:MM*

<Protocol: Janssen OZ1-HV1-101/102/202>

<INC code: 1003733>

<SAP Version: 3.0>

Janssen - OZ1-HVI-101/102/202

TABLE 14.3.5

Page 1 of x

Serious and Non-Serious Related Adverse Events  
Relationship Between Time on Study and Related Serious and Non Serious Adverse Events  
Summary Statistics: Safety Population

Visit		Statistic	OZ1-HV1-102 / OZ1-HV1-202 (N = XX)	Overall (N = XX)
2.5 years post infusion	SAE	N (1) Rho (2) p-value		
	NSRAE	N (1) Rho (2) p-value		
3 years post infusion	SAE	N (1) Rho (2) p-value		
	NSRAE	N (1) Rho (2) p-value		
3.5 years post infusion	SAE	N (1) Rho (2) p-value		
	NSRAE	N (1) Rho (2) p-value		
Etc...	Etc...	Etc...		

Note: Data summarized in this table are presented in data listing x.x  
 (1) N = number of patients experiencing at least one event  
 (2) Rho = Spearman's Rank Correlation co-efficient

DDMMYYYY HH:MM

<Protocol: Janssen OZ1-HV1-101/102/202>

<INC code: 1003733>

<SAP Version: 3.0>

Janssen - OZ1-HV1-101/102/202

TABLE 14.3.6

Page 1 of x

Patient Death  
By System Organ Class, Preferred Term including Patient ID  
Summary Statistics: Safety Population

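### SAP 8.2.5 is headed and tabulated as time on study but its text correlates DNA-PCR %, and the time-on-study Spearman rho does not adjust for time at risk

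*SAP*

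**What the plan says.** The heading of SAP 8.2.5 announces a correlation between event frequency and time on study. The operative sentence names another variable: "Correlation between OZ1 & LNL6 DNA-PCR (%) and the frequency of SAEs and NSRAEs will be assessed using PROC CORR in SAS". The text then asks for a count of those still being followed and of those with an event, the latter worded as "experiencing at least one SAE at the timepoints 2.5, 3, 3.5, 4, 4.5, 5, > 5 to ≤ 10 and > 10", timed in years since infusion. On where the Spearman statistic is given, it says: "rank correlation co-efficient and its associated p-value overall timepoints will be presented". The same is to be done for NSRAEs.

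The second line of the Table 14.3.5 title, in the index and in the shell, is "Relationship Between Time on Study and Related Serious and Non Serious Adverse Events". The shell has no marking variable. It prints N, rho and p for SAE and for NSRAE on each visit row, and footnote 1 defines "N = number of patients experiencing at least one event". Its columns are 102/202 combined and overall, whereas SAP 8.2 states: "The following AE summary tables will be presented 101, 102, 202 and overall".

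The index assigns the table to the Safety population. Person-time enters only in 8.2.4. That section divides related SAEs by total patient-years, counted from two years after infusion, and gives one rate over all follow-up.

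**The concern.** Two different analyses share one section number. Following the operative sentence gives a statistic that does not belong under the table's title. Following the title leaves open whether the correlation runs over patients, patient-visits or timepoints.

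The time-on-study analysis has a further problem: a rank correlation of event frequency with time responds to how long people were observed as well as to any change in risk. Table 14.3.5 is the only SAP table that sets SAEs out by time since infusion. In a delayed-safety study it is where a reader would look for a rising or falling SAE risk, and rho cannot separate that from the pattern of follow-up.

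**Working it through.** The plan gives no event rate, expected correlation or sample size for this analysis, so there is no stated figure to reproduce.

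**1. The places compared**

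- Variable: time on study in the contents list, the 8.2.5 heading, the index and the shell; DNA-PCR % in the operative sentence only. SAP 7.2.1 uses the same PROC CORR formula for marking, reporting "The number of patients with quantifiable detected and calculated dose data" with rho and p. This suggests carried-over text, which is an inference.
- Layout: one rho over all timepoints in the text (the wording is garbled); one per visit row in the shell.
- Unit of analysis: not stated in 8.2.5. Section 7.2.1 works per patient.

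**2. Timepoint totals**

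Six points stand for intervals of about 0.5 years, then come one 5-year interval and one open-ended interval. Assume a constant risk of 0.1 SAE per year:

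- 0.5 years: 1 − exp(−0.1 × 0.5) = 0.0488, or 4.9%
- 5 years: 1 − exp(−0.1 × 5) = 0.3935, or 39.3%
- ratio: 0.3935 / 0.0488 = 8.1, with no change in risk

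At 0.05 and 0.2 per year the ratios are 9.0 and 6.6.

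Spearman's rho of interval order (1 to 8) with these expected proportions under full follow-up: the six short intervals tie at rank 3.5, and the sum of squares for order is 42.

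- Last interval 2 years long: ranks 8 and 7; rho = 23.5 / √(42 × 24.5) = 0.733
- Last interval 5 years long: both rank 7.5; rho = 24 / √(42 × 24) = 0.756

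**3. Per-patient counts**

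At constant risk the expected count is rate × (years followed − 2). The last subject's year 10 falls on 13 Feb 2016 (SAP 1.1 and 6.1), so 30 Nov 2017 is 11.79 years after that infusion. At 0.1 per year, a recipient followed to then expects 0.1 × 9.79 = 0.98 events. A placebo patient leaving 202 at year 4 (assumed) expects 0.1 × 2 = 0.20. Both are in the Safety population of SAP 4.1.

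**4. One row of the shell**

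If time on study means time at that visit, a half-yearly row spans only the ± 6 week window (6 / 52.18 = 0.115 years either way). Rho would have almost no time to correlate with.

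**5. Simulation under constant risk**

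There were 2,000 runs per scenario. Assumed: 37 or 47 patients, 0.05 to 0.2 SAE per year, dropout hazard 0.02 to 0.10 per year, no placebo group. Only the 37 has a basis in the documents (about half of 74, Protocol 1.1).

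| Quantity correlated with time | Mean rho | Runs with p < 0.05 |
|---|---|---|
| Patients with an SAE per timepoint | 0.42 to 0.57 | 14% to 26% |
| Proportion of patients on study with an SAE | 0.55 to 0.63 | 28% to 36% |
| SAE count per patient | 0.18 to 0.62 | 19% to 99.8% |
| Events per patient-year by interval | 0.03 to 0.13 | 3.9% to 6.5% |

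A wider set used 30, 50 or 90 recipients, 0.02 to 0.2 per year, 0 to 20% attrition per year, and either no placebo group or an equal-sized one leaving at 2.5 to 4 years:

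- Per-patient mean rho: 0.03 to 0.12 with neither attrition nor placebo; 0.20 to 0.68 with placebo withdrawal.
- Timepoint counts: 0.52 to 0.59 with neither attrition nor placebo; −0.38 to −0.05 with 20% attrition plus placebo withdrawal.
- Proportions of patients on study: 0.05 to 0.61 over all scenarios.

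**The case against.** The strongest reply is that the intended variable is hardly in doubt: four places say time on study and one sentence disagrees. That stands. A reader might infer that the choice of variable is wholly open, but the documents do not support this. Correcting the sentence is enough.

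The text also reports the number of patients on study, which is an at-risk count. That stands in part: it addresses attrition but not unequal interval length, as the second row of the table shows.

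Three stronger readings of the shell also fall away:

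- **Event set.** A reader might take the word Related in the second title line as restricting the SAEs. The first title line and the SAE and NSRAE row labels match the text, so this is loose wording.
- **N.** A reader might conclude from footnote 1 that rho uses only patients with an event and so could seldom be computed. In the sister shell, Table 14.2.1.2, N counts patients with quantifiable marking even on rows whose chi-square test compares patients with and without it. In these shells N need not be the analysed sample.
- **Columns.** SAP Section 5 plans pooling of 102 and 202 by cell type. The combined column is therefore legitimate, and only the separate study columns are missing.

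The simulation inputs are assumed, and 90 recipients plus as many placebo patients exceeds the 74 planned in the parent trial. The simulations show that rho depends on the follow-up pattern. They do not predict this trial's result.

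**Conclusion.** The point holds. SAP 8.2.5 contradicts its own heading and table on the variable, and its text and shell differ on where rho is given. The unit of analysis is not stated. On the reading the documents best support, rho and its p-value do not adjust for time at risk, whether computed per patient or over the listed timepoints.

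The 4.9% and 39.3% rest on an assumed constant 0.1 SAE per year. A reader might infer that the table will show a false rise in risk. The documents do not support that, because under heavy attrition with placebo withdrawal the timepoint-count correlation turns negative.

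Importance is low to moderate. Protocol 9 makes the analysis mainly descriptive, and no decision rule uses this p-value. Late events also appear in the annual AE summaries (Protocol 9.2), the visit-level clinical-history tables, and the SAE and death listings.

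**What to change.** Correct the operative sentence to time on study, so that heading, text, index and shell agree. Replace rho and p with SAE and NSRAE incidence per patient-year by interval: events over person-years at risk in that interval, with 95% CI. Split the 8.2.4 person-years by interval to supply the denominators. Dividing each patient's count by that patient's own follow-up and rank-correlating the result is not enough: in the first simulation it still gave p < 0.05 in 6.6% to 56.8% of runs.

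Show the Safety population and, separately, the PP population (OZ1/LNL6 recipients, SAP 4.2), which Section 5 already uses for all data. Use columns for 101, 102, 202 and overall, plus the pooled 102/202 column. Tidy the second title line and the N footnote.

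If a marking correlation is also wanted, give it its own section and table. State which marking value is paired with which events and how other results are handled, since SAP 7.1 says: "For samples above the limit of quantification the percentage detected will be recorded for OZ1 & LNL6 DNA-PCR".

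The cost is SAP wording, one index line, one redrawn shell and one extended derivation. No new data are needed.
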